6.3 Modification of Study Intervention/Investigational Product for a Participant

No modifications of the investigational product are anticipated as this is a single dose study.

6.4 Accountability Procedures for the Study Intervention/Investigational Product(s)

Study products will be stored and shipped from the DMID-CMS, [REDACTED], to the participating VTEU. Once received, study products will be stored in and dispensed by the Investigational Pharmacy. Unused product will be handled in accordance with the MOP.

The United States Food and Drug Administration (FDA) requires accounting for the disposition of all investigational products. The Investigator is responsible for ensuring that a current record of product disposition is maintained and product is dispensed only at an official study site by authorized personnel as required by applicable regulations and guidelines. Records of product disposition, as required by federal law, consist of the date received, date administered, quantity administered, and the subject number to whom the drug was administered.

The Investigational Pharmacist will be responsible for maintaining accurate records of the shipment and dispensing of the investigational product. The pharmacy records must be available for inspection by the DMID monitoring contractors, and is subject to inspection by a regulatory agency (e.g., FDA) at any time. An assigned Study Monitor will review the pharmacy records.

Used and unused vials of vaccine and placebo will be retained until clinical trial accountability is completed, monitored and released for disposition as applicable. At study termination, all unused investigational product and VaxINator devices will be handled in accordance with the MOP following complete drug accountability and monitoring.

6.5 Assessment of Subject Compliance with Investigational Product

Subjects will be directly observed at the time of dosing by a member of the clinical research team who is licensed to administer the study product. Administration will be documented on the appropriate data collection form and entered into the eCRF.

6.6 Concomitant Medications/Treatments

Administration of medications, therapies, or vaccines will be recorded on the appropriate data collection form. Concomitant medications will include all current medications and medications taken within 30 days prior to signing the informed consent form through approximately 28 days after study vaccination (or through the early termination visit if prior to that time). Prescription and over-the-counter drugs will be included, as well as herbals, vitamins and supplements. In addition, receipt of non-study vaccines will be solicited through approximately 181 days after study vaccination and reported in the eCRF.

Use of new medication should prompt evaluation for the presence of a new diagnosis of chronic medical disease or condition. Medications that might interfere with the evaluation of the investigational product should not be used during the study-reporting period unless clinically indicated as part of the subject's health care. Use of bronchodilator medication due to wheezing (new prescription or daily use) will be used along with signs and symptoms to define a medically significant wheezing adverse event.

7 STUDY SCHEDULE

7.1 Screening Visit (Visit 00, Screening, Clinic Visit [Window: Day -30 to Day -1])

Potential subjects will be screened for eligibility up to 30 days prior to the administration of the study vaccine. The following activities will be performed:

- Subjects will be provided with a description of this study (purpose and study procedures) and asked to read and sign the informed consent form. The informed consent form will be signed prior to performing any study procedures, including any screening procedures.
- Demographic information will be obtained by interview of subjects.
- Eligibility criteria will be reviewed with subjects.
- Complete medical history will be obtained by interview of subjects to ensure eligibility.
- All concomitant medications taken and vaccines received within 30 days prior to signing the informed consent form will be reviewed with subjects and reported in the electronic Case Report File (eCRF).
- Vital signs, including oral temperature, pulse, and blood pressure, will be obtained to ensure eligibility. Subjects must not eat or drink anything hot or cold, or smoke within 10 minutes prior to taking oral temperature.
- A physical examination will be performed by a study clinician licensed to make medical diagnoses and listed on the Form FDA 1572 as the site principal investigator or sub-investigator.
- A urine or serum pregnancy test will be performed on all women of childbearing potential and must be negative to ensure eligibility.
- Approximately 10 mL of venous blood will be collected for complete blood count, serum chemistries and HIV antibody testing.
- Approximately 5 mL of venous blood will be collected for screening antibody assays (PT and PRN serum IgG).
- Nasal samples will be obtained for baseline mucosal antibody assays.

7.2 Enrollment/Vaccination (Visit 1, Clinic Visit [Day 1])

- Subject's willingness to participate will be reconfirmed and documented in the subject's study records prior to performing any further study procedures, including administration of the study vaccination.
- Eligibility criteria will be reviewed with subjects prior to study vaccination to ensure continued eligibility.
- Complete medical history and any updates obtained by interview of subjects since the screening visit will be reviewed with subjects prior to study vaccination to ensure continued eligibility.
- All concomitant medications will be reviewed with subjects prior to study vaccination for accuracy and completeness. Any new concomitant medications taken since the screening visit will be reviewed with subjects and assessed for continued eligibility prior to study vaccination. Medications reported in the eCRF are limited to those taken within 30 days prior to study vaccination.
- Vital signs, including oral temperature, pulse, and blood pressure, will be obtained prior to study vaccination. Vital signs assessed on Day 1 will be considered as baseline. Subjects must not eat or drink anything hot or cold, or smoke within 10 minutes prior to taking oral temperature.
- A limited physical examination will be performed, focused on the nasopharynx, oropharynx, and lungs prior to study vaccination; in addition, a targeted physical examination will be performed, if indicated, based on review of interim medical history, by a study clinician.
- A urine or serum pregnancy test will be performed within 24 hours prior to study vaccination on all women of childbearing potential. Results must be negative and known prior to randomization and first study vaccination.
- Approximately 10 mL of venous blood will be collected immediately prior to study vaccination for baseline antibody assays.
 - For subjects who consent to additional future use samples, approximately 24 mL of venous blood will be collected immediately prior to study vaccination for PBMC isolation and possible future research.

-
- Subjects will be enrolled in AdvantageEDCSM and assigned randomly to a treatment arm prior to study vaccination.
 - Pre-administration reactogenicity assessments will be performed prior to vaccination to establish baseline. Subjects will then receive a single dose of study vaccine via intranasal application. Subjects will be observed in the clinic for two (2) hours to record post-administration reactogenicity and any AE/SAEs will be recorded on the appropriate data collection form prior to discharge from the clinic.
 - Subjects will be provided with a memory aid and other study-related materials to record daily oral temperature, solicited mucosal and systemic reactions, any unsolicited AEs, and concomitant medications. Subjects will be encouraged to take their oral temperature around the same time each day. Subjects must not eat or drink anything hot or cold, or smoke within 10 minutes prior to taking oral temperature. Subjects will be instructed on how to use their memory aid and how to measure and record AEs prior to discharge from the clinic. Subjects will be instructed to notify the study center if they develop any severe reactions after study vaccination. If the site principal investigator or appropriate sub-investigator deems the reaction severe enough, further instructions will be given to the subject on the proper course of action, including a return to the clinic for immediate evaluation if appropriate.

7.3 Follow-up Visits

7.3.1 Visit 2, Day 8, Clinic Visit (Window: Day 8 ± 2 days)

- Interim medical history, including an assessment for new medical conditions, will be obtained by interview of subjects and any changes since the previous clinic visit or contact will be noted.
- Memory aid information will be reviewed with subjects.
- All concomitant medications and vaccines will be recorded on the appropriate data collection form.
- All AE/SAEs will be recorded on the appropriate data collection form.
- A limited physical examination will be performed, focused on the nasopharynx, oropharynx, and lungs; in addition, a targeted physical examination will be performed, if indicated, based on review of interim medical history, by a study clinician.

-
- Approximately 10 mL of venous blood will be collected for safety laboratory studies, to include a complete blood count (white blood cell count, platelet count, hemoglobin concentration) and serum chemistries (ALT and creatinine)
 - For subjects who consent to additional future use samples, approximately 24 mL of venous blood will be collected for PBMC isolation and possible future research.

7.3.2 Visit 3, Day 15, Clinic Visit (Window: Day 15 ± 3 days)

- Interim medical history, including an assessment for new medical conditions, will be obtained by interview of subjects and any changes since the previous clinic visit or contact will be noted.
- All concomitant medications and vaccines will be recorded on the appropriate data collection form.
- Memory aid information will be reviewed with subjects.
- All AE/SAEs will be recorded on the appropriate data collection form.
- A limited physical examination will be performed, focused on the nasopharynx, oropharynx, and lungs; in addition, a targeted physical examination will be performed, if indicated, based on review of interim medical history, by a study clinician.
- Approximately 10 mL of venous blood will be collected for antibody assays.

7.3.3 Visit 4, Day 29, Clinic Visit (Window: Day 29 ± 3 days)

- Interim medical history, including an assessment for new medical conditions, will be obtained by interview of subjects and any changes since the previous clinic visit or contact will be noted.
- All concomitant medications and vaccines will be recorded on the appropriate data collection form.
- All AE/SAEs will be recorded on the appropriate data collection form.
- A targeted physical examination may be performed, if indicated based on review of interim medical history, by a study clinician.
- Approximately 10 mL of venous blood will be collected for antibody assays.

-
- For subjects who consent to additional future use samples, approximately 24 mL of venous blood will be collected for PMBC isolation and possible future research.
 - Nasal samples will be obtained for *B. pertussis* culture and immunological assays. If culture is positive for *B. pertussis*, the isolate will be cryopreserved as detailed in the MOP.

7.3.4 Visit 4a (If needed, based on *B. pertussis* positive culture on Day 29), Day 46, Clinic Visit (Day 46 ± 3 days)

- Interim medical history, including an assessment for new medical conditions, will be obtained by interview of subjects and any changes since the previous clinic visit or contact will be noted.
- All concomitant vaccines will be recorded on the appropriate data collection form.
- All SAEs will be recorded on the appropriate data collection form.
- A targeted physical examination may be performed, if indicated based on review of interim medical history, by a study clinician.
- Nasal samples will be obtained for *B. pertussis* culture (if necessary-positive from day 29) and immunological assays. If culture is positive for *B. pertussis*, the isolate will be cryopreserved as detailed in the MOP.

7.3.5 Visit 4b (if needed, based on positive *B. pertussis* culture from Day 46), Day 50, Phone Call (Day 50 ± 3 days)

- If a participant's sample from Visit 4a is positive for *B. pertussis*, a study investigator will prescribe a 5-day course of azithromycin (500 mg orally once per day).

7.4 Final Study Visit, Visit 5, Day 181, Clinic Visit (Day 181 ± 21 days)

- Interim medical history, including an assessment for new medical conditions, will be obtained by interview of subjects and any changes since the previous clinic visit or contact will be noted.
- All concomitant vaccines will be recorded on the appropriate data collection form.
- All SAEs will be recorded on the appropriate data collection form.

-
- A targeted physical examination may be performed, if indicated based on review of interim medical history, by a study clinician.
 - Approximately 10 mL of venous blood will be collected for antibody assays.
 - For subjects who consent to additional future use samples, approximately 24 mL of venous blood will be collected for PBMC isolation and possible future research.
 - Nasal samples will be obtained for immunological assays

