To minimize the risk of transmission, the volunteers will stay at the study center for 2 hours after administration of the vaccine. In addition, volunteers with household or professional contact with infants below one year of age or household/professional contact with individuals with immunodeficiency will be excluded from participation in the study. The attenuated BPZE1 bacteria colonize the upper respiratory tract similarly to wild-type *B. pertussis*. Colonization of live organism will be assessed from a nasopharyngeal swab performed 28 days after administration to ensure all subjects are cleared of colonization. If a subject is not clear at day 29, a repeat nasal swab and culture will be performed at day 46. Chronic carriage of BPZE1 has not been reported (i.e., the vast majority of subjects have been clear at day 29 and no subject has had positive cultures at day 46) and is therefore not expected. Any subject who remains positive at day 46 will be provided a short course of azithromycin, which is clinically used to eradicate *B. pertussis* from the nasopharynx. Azithromycin will be prescribed by a study physician and filled by the hospital pharmacy or the patient's desired pharmacy at no cost to the subject.

Furthermore, in animal studies, when female mice were vaccinated with BPZE1 shortly before mating, no negative effect on either the pregnancy or their offspring was observed. The offspring were protected against *B. pertussis* challenge, based on evaluation of the lungs at necropsy.[16]

[REDACTED]

2.3.1.3 Risks to the Environment or Potential for Interaction with wild-type *B. pertussis* strains

Detailed information about the [REDACTED] BPZE1 is available in the environment risk assessment located in the investigator's brochure.

To avoid accidental exposure to the environment and to study staff, actions should be taken to minimize generation of aerosols, since the bacteria are strictly respiratory tract organisms. Staff members should wear eye-protective glasses during the vaccination. Persons handling BPZE1 should wear gloves and must practice standard hand hygiene before touching their skin or eyes.

[REDACTED]

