⁷ *Close contact includes sharing a household, serving as a healthcare worker, or working professionally in settings with repeated exposures.*

19. Receipt of *B. pertussis*-active antibiotics⁸ within 7 days prior to vaccination

⁸ *B. pertussis* active antibiotics include macrolides, fluoroquinolones, trimethoprim-sulfamethoxazole, tetracyclines

20. Known hypersensitivity to any component of the study vaccine.

21. Hypersensitivity to azithromycin, which may be used in the event of ongoing BPZE1 colonization

22. Any condition that, in the opinion of the investigator, might interfere with objectives of the study or safety to the individual

23. Acute illness, including temperature >100°F within one week prior to vaccination⁹

⁹ *Enrollment may be postponed if acute illness occurs; subjects must remain within the screening window, however, and must be rescreened if >30 days elapses prior to enrollment.*

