& Inclusive of reactogenicity assessments performed on the day of study vaccination through 14 days after study vaccination.

** Assessment of AE/SAE limited to new-onset chronic medical conditions, AESI, and SAEs if after 28 days following the study vaccination.

- ² To be performed locally by the site, and will include white blood cell count, hemoglobin, platelet count, alanine aminotransferase, serum creatinine, and HIV screening
- ^Ω Venous blood will only be obtained if the early termination visit occurs: 1) prior to Visit 2, 2) after day 14 post-vaccination but before Visit 3, or 3) at least 28 days following Visit 3.
- * See Schedule of Events secondary table for Visits 4a and 4b.

| Study Visit Number | V4a* | V4b** (Phone call) |
|--|--------|-----------------------|
| Study Day post study vaccination | D46±3d | Day 50 ± 3 days |
| Nasal Sample Collection for B. pertussis Culture and immunological assays | X | |
| Prescription of Azithromycin 500 mg by mouth once daily | | X |
| Interim Medical History | X | |
| SAE Assessment | X | |
| Targeted Physical Examination, if indicated | X | |
| Concomitant Non-study Vaccines | X | |

*Study visit only if nasal sample is positive for *B. pertussis* at Day 29

**Study visit only if nasal sample is positive for *B. pertussis* at Day 46

Venipuncture Volumes (mL)

| Study Visit Number | V00 | V01 | V02 | V03 | V04 | V05 | Early Termination (if needed) | Unscheduled (if needed) |
|--|-------------------------|-----------------------------|-----------|-----------|-----------|-----------|-------------------------------|-------------------------|
| Study Day post study vaccination | Screening (D-30 to D-1) | Enrollment and Dose 1 D1 | D8±2d | D15±3d | D29±3d | D181±21d | | |
| Venous Blood Collection for Screening Laboratory Assays ² | 10 | 0 | 0 | 0 | 0 | 0 | 0 | 0 |
| Venous Blood Collection for Safety Laboratory Assays | 0 | 0 | 10 | 0 | 0 | 0 | 0 | 0 |
| Venous Blood Collection for Serum Antibody Assays ³ | 5 | 10 | 0 | 10 | 10 | 10 | 10 | 0 |
| Venous Blood Collection for PBMC isolation and Future Research | 0 | 24 | 24 | 0 | 24 | 24 | 24 | 0 |
| Maximum Total* | 15 | 34 | 34 | 10 | 34 | 34 | 34 | 0 |

*Maximum total for up to 6 study visits (161 mL).

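### Visit 4a (Day 46) does not record concomitant medications or new acute non-serious adverse events in subjects still culture-positive at Day 29, so a Day 46 negative cannot be told apart from clearance by an outside antibiotic

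*Protocol*

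**What the plan says.** Protocol 7.3.4 sets out what happens at Visit 4a. There is a history: "Interim medical history, including an assessment for new medical conditions, will be obtained by interview of subjects". For treatments: "All concomitant vaccines will be recorded on the appropriate data collection form". For events: "All SAEs will be recorded on the appropriate data collection form". A targeted examination is done if indicated, and nasal samples are taken for culture and immunological assays. The secondary schedule in Appendix A agrees. Its only row for treatments received is "Concomitant Non-study Vaccines", and it has no row for non-serious AEs or for medications. SAP Table 2 has neither row, and it also leaves out the vaccine row.

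The general windows are not extended for carriers. Protocol 6.6 collects "medications taken within 30 days prior to signing the informed consent form through approximately 28 days after study vaccination". Sections 9.1 and 9.4 end collection of unsolicited non-serious AEs at about 28 days. Early termination and unscheduled visits (7.5, 7.6) record only SAEs after 28 days, and medications only before Day 29.

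The Day 46 culture in subjects positive at Day 29 is part of the third secondary outcome (Protocol 3.2.2; SAP 3.2.2). It is to be tabulated in SAP Table 33 and listed in SAP Listing 13. Exclusion 19 in Protocol 5.2 names the relevant drugs: "active antibiotics include macrolides, fluoroquinolones, trimethoprim-sulfamethoxazole, tetracyclines". It applies only to the 7 days before vaccination.

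**The concern.** For a live vaccine, exposure lasts as long as colonisation does. The protocol identifies the subjects whose exposure has outlasted the standard 28-day window and brings them back, but the two kinds of data most relevant to them stop just as that period begins.

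Two things follow. First, the Day 46 culture is meant to show whether BPZE1 has cleared. A carrier who takes a macrolide or another listed antibiotic for an unrelated illness between the two cultures may test negative because of the drug, and would be counted as cleared like anyone else. Second, a new sinus, throat or nasal complaint in a known carrier may be mentioned in the interim history but does not become an AE. The halting rules in Protocol 9.5 cover nasal ulceration, abscess or necrosis related to study product through the subject's last visit. Such a lesion need not be an SAE, so the rule runs past the date at which the events that could trigger it are recorded.

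**Working it through.** The plan states no figure on this point, so the check is mainly a comparison of what each section collects.

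**Step 1. What changes between the two visits**

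| Item | Visit 4, Day 29 (7.3.3) | Visit 4a, Day 46 (7.3.4, Appendix A) |
|---|---|---|
| Interim history with new conditions | yes | yes |
| Targeted examination if indicated | yes | yes |
| SAEs | yes | yes |
| New acute non-serious AEs | yes | no |
| Non-study vaccines | yes | yes |
| Concomitant medications | yes | no |
| Nasal culture | yes | yes |

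**Step 2. Does another section restore the missing items?**
- Medications: 6.6 and 8.1 stop at about 28 days, and SAP 4.4.7 and 9.1.2 do the same. Sections 7.5 and 7.6 collect them only before Day 29.
- Non-serious AEs: 9.1 and 9.4 stop at about 28 days. After that, 7.5 and 7.6 record SAEs only.
- What continues: new onset chronic medical conditions to Day 181 (9.2.4), and follow-up of AEs that have already begun to stabilisation or resolution (9.2.1).

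Neither missing item is restored.

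**Step 3. Could the analysis deal with it?**
- The per-protocol exclusions (Protocol 11.4.1.3; SAP 6.3.3) are given as examples, and antibiotics are not among them. They could be added, but an exclusion cannot be applied to a drug that was not recorded.
- Listing 13 has columns for group, subject, planned time point, study day and culture result. None is for antibiotic use.
- If anyone is colonised at Day 29, Protocol 11.4 extends the primary database to about Day 46, but the AE data in it remain 28-day data.

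**Step 4. Length of the gap**
- Nominal: 46 − 29 = 17 days.
- Shortest with ±3-day windows: (46 − 3) − (29 + 3) = 43 − 32 = 11 days.
- Longest: (46 + 3) − (29 − 3) = 49 − 26 = 23 days.
- Share of Day 1 to Day 46: 17/45 = 38%.

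**Step 5. How many subjects (assumption)**

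The documents give no Day 29 carriage rate for this formulation. BPZE1 recipients number 15 + 15 + 5 = 35. For an assumed rate p, the expected number is 35p and the chance of at least one carrier is 1 − (1 − p)^35.

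| p | Expected carriers | Chance of at least one |
|---|---|---|
| 2% | 0.7 | 51% |
| 5% | 1.75 | 83% |
| 10% | 3.5 | 97.5% |
| 20% | 7 | >99% |

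Over this range the likely number runs from none to a handful. The Day 46 result is then close to a set of individual case reports. For example, if three carriers were all negative, the exact 95% upper limit would be 1 − 0.025^(1/3) = 71%. The proportion itself says little, so the value lies in knowing how each negative came about.

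**The case against.** The case for leaving the plan alone has weight. The 28-day window is a prespecified primary outcome and is applied consistently, so this is a gap in design and not a contradiction. There may be no carriers. Protocol 2.3.1.2 says that the vast majority of earlier subjects were clear at Day 29 and none was positive at Day 46, so a positive masked by an antibiotic is improbable. Section 6.6 discourages interfering drugs unless clinically indicated, and the interim history may bring a treated illness to light. Extended collection would be uncontrolled, because placebo recipients are not expected to carry the strain. All of this stands and limits the size of the point. It does not give an outside antibiotic or a new acute event a place to be recorded.

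Four stronger readings are tempting, and the documents do not support them.
- A reader might infer that Visit 4a records only SAEs and vaccines. Interim history, an examination if indicated and nasal samples are also specified.
- A reader might infer that carriers have no non-serious safety data. They have solicited data to 14 days and unsolicited data to about Day 29, follow-up of events that began by then, and chronic conditions to Day 181.
- A reader might infer that one unrecorded antibiotic course would shift the Day 46 proportion greatly. That needs an assumed handful of carriers as the denominator and a subject who would otherwise have stayed positive. The carrier count is not given, no Day 46 positive has been reported, and SAP Table 33 defines N as the per-protocol population. One subject in an arm of 15 is 1/15 = 6.7 points.
- A reader might infer that study azithromycin confuses the clearance result. It is for a subject still positive at Day 46 ("Any subject who remains positive at day 46 will be provided a short course of azithromycin"), and no later culture is scheduled.

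**Conclusion.** The point holds as a limited gap in data collection. For subjects culture-positive at Day 29, new acute non-serious AEs and concomitant medications are not recorded between about Day 29 and Visit 4a. A Day 46 negative in such a subject cannot be separated from clearance by an outside *B. pertussis*-active antibiotic. A new acute non-serious event has no AE record, while the nasal-lesion halting rule is still running.

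The gap is 17 days nominally and 11 to 23 days with visit windows. This is an upper bound on carriage before Day 46, because a positive Day 29 culture shows carriage on that day only and the subject may have cleared soon after. The number affected is not stated and may be zero; the carriage rates above are assumptions. The randomised 28-day safety comparison is not affected. What suffers is the interpretation of the Day 46 part of a secondary outcome, and safety capture in the few subjects whose carriage lasts longest.

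**What to change.** In Protocol 6.6, 7.3.4 and Appendix A, and in SAP Table 2, add for subjects culture-positive at Day 29:
1. Recording of concomitant medications from Day 29 through Visit 4a, with *B. pertussis*-active antibiotics identified by the list already in Protocol 5.2.
2. Recording of all AEs over the same period.
3. A separate listing of these AEs and medications, so that the 28-day comparison between arms is unchanged.
4. A flag in SAP Table 33 and Listing 13 on any Day 46 negative that follows an active antibiotic, so that it is not read as natural clearance.

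The windows for adverse events of special interest should be reconciled at the same time. Protocol 9.2.5 ends wheezing assessment at Day 29, the Appendix A footnote keeps AESIs among the events assessed after 28 days, and 15.4 expects their assessment until the final follow-up visit. The non-study vaccine row missing from SAP Table 2 can be restored in the same edit.

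The cost is two existing forms completed at a visit that already takes place, one listing and some SAP wording. The downside is longer and uncontrolled ascertainment in a few subjects, which is why those data should be listed apart and not pooled with the 28-day summaries.
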